| 10.3.2.1. Pharmacokinetic Parameter Estimation | 41 |
| 10.3.2.2. Pharmacokinetic Statistical Inference | 41 |
| 10.3.3. Pharmacodynamic Analyses | 42 |
| 10.3.4. Pharmacokinetic/Pharmacodynamic Analyses | 42 |
| 10.3.5. Evaluation of Immunogenicity | 42 |
| 10.3.6. Interim Analyses | 42 |
| 11. References | 44 |

List of Tables

| Table | | Page |
|---------------|---|-------------|
| Table AMAL.1. | Objectives and Endpoints | 17 |
| Table AMAL.2. | Margin of Safety for Intravenous Administration of LY3074828 Based on Administered Dose and Predicted Exposure | 20 |
| Table AMAL.3. | Treatments Administered..... | 27 |

List of Appendices

| Appendix | | Page |
|-----------------|---|-------------|
| Appendix 1. | Abbreviations and Definitions | 46 |
| Appendix 2. | Clinical Laboratory Tests..... | 50 |
| Appendix 3. | Study Governance, Regulatory and Ethical Considerations | 51 |
| Appendix 4. | Blood Sampling Summary | 54 |

1. Protocol Synopsis

Title of Study:

A Phase 1, Single-Dose Study to Assess the Relative Bioavailability, Absolute Bioavailability, and Tolerability of LY3074828 Formulations in Healthy Subjects

Rationale:

Study I6T-MC-AMAL (AMAL) is a Phase 1 study designed to compare the formulation of LY3074828 previously used in Phase 1 and 2 studies with the formulation proposed for Phase 3 studies. Study AMAL will determine whether the pharmacokinetics (PK) and tolerability of LY3074828 are affected following changes to the investigational product, when administered subcutaneously to healthy subjects. The potential effect of administering the same volume as a single injection ($1 \times 2\text{-mL}$) or as 2 injections ($2 \times 1\text{-mL}$) on PK and tolerability will also be investigated during subcutaneous (SC) administration. In addition, the absolute bioavailability of LY3074828 Drug Product produced by the new process will be investigated by inclusion of an intravenous (IV) LY3074828 treatment.

Objective(s)/Endpoints:

| Objectives | Endpoints |
|---|--|
| Primary To evaluate the relative bioavailability of the LY3074828 lyophilized formulation prepared by reconstitution (Reference) and the extemporaneously prepared formulation (SC $2 \times 1\text{-mL}$) when administered to healthy subjects by SC injection. | Reference versus SC $2 \times 1\text{-mL}$. The ratio of geometric least squares means between the test and reference formulations will be calculated for key PK parameters of LY3074828. Primary endpoints will be area under the concentration versus time curve (AUC) from time zero to infinity ($\text{AUC}[0-\infty]$) and AUC from time zero to time t , where t is the last sample with a measurable concentration ($\text{AUC}[0-t_{\text{last}}]$). The secondary endpoints will be maximum observed drug concentration (C_{max}) and time to C_{max} (t_{max}). |
| Secondary To evaluate the relative bioavailability of LY3074828 extemporaneously prepared as the test formulation when the same volume is administered to healthy subjects by SC injection using a single injection ($1 \times 2\text{-mL}$) and 2 injections ($2 \times 1\text{-mL}$). To evaluate the absolute bioavailability of LY3074828 extemporaneously prepared as the test formulation when administered to healthy subjects by SC injection compared to IV infusion. | SC $2 \times 1\text{-mL}$ versus SC $1 \times 2\text{-mL}$ of test formulation. The ratio of geometric least squares means between the SC $2 \times 1\text{-mL}$ and SC $1 \times 2\text{-mL}$ injections will be calculated for key PK parameters of LY3074828. Primary endpoints will be $\text{AUC}(0-\infty)$ and $\text{AUC}(0-t_{\text{last}})$. The secondary endpoints will be C_{max} and t_{max} . SC $2 \times 1\text{-mL}$ versus IV and SC $1 \times 2\text{-mL}$ versus IV. The ratio of geometric least squares means of the formulations (SC/IV) will be calculated for $\text{AUC}(0-\infty)$. |
| To assess the impact of Drug Product formulation changes and number of injections on tolerability of LY3074828. | All treatments. Incidence of treatment-emergent adverse events (TEAEs) Incidence of treatment-emergent anti-drug antibodies (TE-ADAs) |

Summary of Study Design:

Study AMAL is a single-center, randomized, parallel-treatment, open-label, Phase 1 single-dose administration study evaluating LY3074828 in healthy subjects.

Subjects will report to the clinical research unit (CRU) on Day –1 and remain at the CRU until after the scheduled procedures have been completed on Day 2. After randomization, study drug will be administered by either IV or SC injection in the morning of Day 1 after an overnight fast.

Safety will be explored by clinical laboratory tests, vital signs measurements, 12-lead electrocardiograms (ECGs), recording of adverse events (AEs), and immunogenicity assessments.

Treatment Arms and Duration:

Subjects will each receive a single dose of LY3074828 and will be randomized to 1 of 4 treatments as follows:

- **Reference:** 250 mg LY3074828; lyophilized formulation with $2 \times 1\text{-mL} + 1 \times 1.5\text{-mL}$ SC injections;
- **Test SC $2 \times 1\text{ mL}$:** 250 mg LY3074828; test formulation with $2 \times 1\text{-mL}$ SC injections;
- **Test SC $1 \times 2\text{ mL}$:** 250 mg LY3074828; test formulation with $1 \times 2\text{-mL}$ SC injection;
- **Test IV:** 250 mg LY3074828; test formulation by IV infusion over at least 30 minutes.

Number of Subjects:

A total of 72 subjects will be enrolled to ensure that approximately 64 subjects complete the study (16 completers per treatment). Study completion is defined as completing all activities up to and including at least Study Day 29.

Statistical Analysis:

Pharmacokinetic parameter estimates will be evaluated to delineate effects of LY3074828 formulation when administered to healthy subjects by SC injection (Reference and SC $2 \times 1\text{-mL}$). Log-transformed C_{\max} , $AUC(0-\infty)$, and $AUC(0-t_{\text{last}})$ estimates will be evaluated in a linear fixed-effect model with a fixed effect for formulation. The differences between the test (SC $2 \times 1\text{-mL}$) compared to the reference formulation will be back-transformed to present the ratios of geometric least squares means and the corresponding 90% confidence interval (CI).

The t_{\max} will be analyzed using a Wilcoxon rank sum test. Estimates of the median difference, 90% CIs, and p-values from the Wilcoxon rank sum test will be calculated.

Similar analyses to those described above will be conducted to delineate the effect of administering the same volume as a single injection (SC $1 \times 2\text{-mL}$) or as 2 injections (SC $2 \times 1\text{-mL}$).

In order to evaluate absolute bioavailability, a fixed-effect model will be used to analyze the log-transformed $AUC(0-\infty)$ and $AUC(0-t_{\text{last}})$ of LY3074828. The model will contain formulation (SC or IV) as a fixed effect. The absolute bioavailability will be estimated for the ratio of the least-squares geometric means of the formulations (SC/IV). The corresponding 90% CI of the ratios will also be estimated. Data from Test IV will be used for the IV formulation (reference). If the number of injections is not observed to have an effect based on the analyses described above, data from SC $2 \times 1\text{-mL}$ and SC $1 \times 2\text{-mL}$ will be combined and used for the SC formulation (and will be considered the primary analysis). If the number of injections is observed to have an effect (SC $2 \times 1\text{-mL}$ versus SC $1 \times 2\text{-mL}$ comparison), analyses to evaluate absolute bioavailability will be done separately

(ie, SC 2 × 1-mL versus IV and SC 1 × 2-mL versus IV). The primary analysis will be considered as that including SC 1 × 2-mL.

Where possible, a single linear model with contrasts to test the different objectives will be used.

Additional analyses may be conducted if they are deemed appropriate.

2. Schedule of Activities

Study Schedule Protocol I6T-MC-AMAL

| Study Day | Screening ≤ 28 days | -1 | 1 | 2 | 4 ±1d | 8 ±1d | 11 ^a ±2d | 15 ±2d | 22 ±2d | 29 ±2d | 43 ±2d | 57 ±3d | 71 ±3d | 85 ±3d | FU/ED ^d | Comment |
|--|------------------------|----|---|----|----------|----------|------------------------|-----------|-----------|-----------|-----------|-----------|-----------|-----------|--------------------|---|
| Informed consent (written) | X | | | | | | | | | | | | | | | |
| Review / confirm inclusion/exclusion criteria | X | X | | | | | | | | | | | | | | Any time prior to dosing |
| Admission to CRU | | X | | | | | | | | | | | | | | |
| Discharge from CRU | | | | X | | | | | | | | | | | | |
| Medical history | X | | | | | | | | | | | | | | | |
| Outpatient visit | X | | | | X | X | X | X | X | X | X | X | X | X | X | |
| Weight / height | X | | | | | | | | | X | | | | X | X | Height at screening only. |
| Vital signs: blood pressure, pulse rate, temperature (hour) | X | | Predose, end of infusion ^b , 2, 6 | 24 | 72 | 168 | 240 | 336 | 504 | 672 | 1008 | | | 2016 | X | Times are referenced to start of dosing. Single ECGs will be collected. Time allowance for 2, 6, and 24 hour time points will be ±15 minutes, ±30 minutes and ±90 minutes respectively. End of infusion vital signs and ECG should be taken 5 to 15 minutes after the end of infusion. |
| 12-lead ECG (hour) | X | | Predose, end of infusion ^b , 2, 6 | 24 | 72 | 168 | | 336 | | 672 | | | | 2016 | X | |
| Physical examination / Medical assessment | X | X | | X | | | | | | | | | | X | X | Full physical examination/ medical assessment at screening, Day -1, ED. Symptom directed physical examination/ medical assessment at all other time points, and as deemed necessary by the investigator. |
| AE review | X | X | X | X | X | X | X | X | X | X | X | X | X | X | X | AE only after signing ICF |
| QuantiFERON®-TB Gold test | X | | | | | | | | | | | | | | | |
| Pregnancy test ^c | X | X | | | | | | | | X | | X | | X | X | Women of childbearing potential only. Serum pregnancy test at screening, urine at other times. A positive urine pregnancy test will be confirmed with a serum pregnancy test. |
| Clinical laboratory tests | X | X | | | X | | | | X | | X | | X | X | X | Urine ethanol and drug screen performed at screening and Day -1 during CRU |

| Study Day | Screening ≤ 28 days | -1 | 1 | 2 | 4 ± 1 d | 8 ± 1 d | 11 ^a ± 2 d | 15 ± 2 d | 22 ± 2 d | 29 ± 2 d | 43 ± 2 d | 57 ± 3 d | 71 ± 3 d | 85 ± 3 d | FU/ED ^d | Comment |
|---|--------------------------|----|---|----|-------------|-------------|---------------------------|--------------|--------------|--------------|--------------|--------------|--------------|--------------|--------------------|--|
| | | | | | | | | | | | | | | | | admission, and may be repeated at the discretion of the investigator. |
| LY3074828 dose | | | X | | | | | | | | | | | | | |
| Injection / infusion-site assessment for erythema, induration, categorical pain, pruritus, and edema (hour) | | | 0, 0.25 ^e , end of infusion ^b | 24 | | 168 | | 336 | | | | | | | | Times are referenced to start of dosing. 0 hour assessments should be performed within 5 minutes after giving all SC injections or start of IV infusion. End of infusion assessments should be completed within 5 minutes after infusion. Additional assessments may be performed if deemed necessary by the investigator. |
| Injection site pain based on Visual analog scale (VAS) (hour) | | | 0, 0.5, 1, 3, 6 | 24 | | | | | | | | | | | | Performed only on subjects randomized to Test SC 2 x 1 mL (assessed for the first of 2 injections) and Test SC 1 x 2 mL only. 0 hour assessments should be performed within 1 minute after injection. Time allowance for 0.5 and 1 hour will be ± 5 minutes and all other time allowance will be ± 15 minutes. |
| Injection site leakage and bleeding assessment (hour) | | | 0 | | | | | | | | | | | | | Performed only on subjects randomized to Test SC 2 x 1 mL and Test SC 1 x 2 mL only. 0 hour assessments should be performed within 1 minute after injection. |
| LY3074828 PK sampling (hour) | | | 0, end of infusion ^b , 2, 6 | 24 | 72 | 168 | 240 | 336 | 504 | 672 | 1008 | 1344 | 1680 | 2016 | X | Times are referenced to start of dosing. 0 hour collection should be taken immediately (within 15 minutes) before dosing. The end of infusion sampling should be taken at the end of IV infusion. Time allowance for 2, 6, and 24 hour time points will be ± 15 , ± 30 , and ± 90 minutes respectively. |

| Study Day | Screening ≤ 28 days | -1 | 1 | 2 ±1d | 4 ±1d | 8 ±2d | 11 ^a ±2d | 15 ±2d | 22 ±2d | 29 ±2d | 43 ±2d | 57 ±3d | 71 ±3d | 85 ±3d | FU/ED ^d | Comment |
|-------------------------|------------------------|----|---------|----------|----------|----------|------------------------|-----------|-----------|-----------|-----------|-----------|-----------|-----------|---------------------------|---------|
| Immunogenicity sample | | | Predose | | | | X | | X | | | | X | X | LY3074828 antibody sample | |
| Pharmacogenetics sample | | X | | | | | | | | | | | | | For storage only. | |

Abbreviations: AE = adverse event; CRU = clinical research unit; d = day; ECG = electrocardiogram; ED = early discontinuation; FU = follow-up visit; ICF = informed consent form; IV = intravenous; PK = pharmacokinetic; TB = tuberculosis; VAS = visual analog scale.

Site should schedule activities as appropriate. In cases where several study procedures are scheduled at the same time, follow this order of priority for procedures: PK samples, ECG, vital signs, clinical laboratory tests, VAS, injection site leakage assessment, injection / infusion site assessment, immunogenicity sample, stored sample. Procedures specified as predose may be performed within 2 hours from planned dosing.

- a Day 11 required for subjects receiving subcutaneous treatments only.
- b Required for subjects receiving IV treatments only.
- c All female subjects of childbearing potential will have serum pregnancy test at screening. For women who are considered to be postmenopausal, follicle-stimulating hormone should be drawn to confirm postmenopausal status as defined in inclusion criterion [1b]; women with confirmed postmenopausal status can be exempted from further pregnancy tests during the study.
- d Within 7 to 14 days after the last procedure or upon ED.
- e Required for subjects receiving SC treatments only – time allowance of ±5 minutes.

3. Introduction

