| 
Secondary
 
To evaluate the relative bioavailability of LY3074828 extemporaneously prepared as the test formulation when the same volume is administered to healthy subjects by SC injection using a single injection (1 × 2-mL) and 2 injections (2 × 1-mL).
 
To evaluate the absolute bioavailability of LY3074828 extemporaneously prepared as the test formulation when administered to healthy subjects by SC injection compared to intravenous (IV) infusion.
 
To assess the impact of Drug Product formulation changes and number of injections on tolerability of LY3074828.
 | 
SC 2 × 1-mL versus SC 1 × 2-mL of test formulation.
 
The ratio of geometric least squares means between the SC 2 × 1-mL and SC 1 × 2-mL injections will be calculated for key PK parameters of LY3074828.
 
Primary endpoints will be AUC(0-∞) and AUC(0-t_{last}).
 
The secondary endpoints will be C_{max} and t_{max}.
 
SC 2 × 1-mL versus IV; SC 1 × 2-mL versus IV.
 
The ratio of geometric least squares means of the formulations (SC/IV) will be calculated for AUC(0-∞).
 
All treatments.
 
Incidence of treatment-emergent adverse events (TEAEs).
 
Incidence of treatment-emergent anti-drug antibodies (TE-ADAs).
 |

5. Study Design

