| Regimen | 250 mg SC ^a | 250 mg SC | 250 mg SC | 250 mg IV |
| Drug Product formulation | reference | test | test | test |
| LY3074828 concentration | 72 mg/mL | 125 mg/mL | 125 mg/mL | 250 mg/10 mL (25 mg/mL) |
| Volume per dose | 2 × 1 mL + 1 × 1.5 mL (3.5 mL total) | 2 × 1 mL (2 mL total) | 1 × 2 mL (2 mL total) | 10 mL infusion |
| Infusion or injection duration | NA | NA | Slow versus fast ^b | ≥30 minutes |

Abbreviations: IV = intravenous; NA = not applicable; SC = subcutaneous.

a Theoretical total dose 252 mg for Reference.

b Odd number subjects will be injected slowly, approximately over 15 seconds and even number subjects will receive the injection over 5 to 10 seconds.

The investigator or designee is responsible for:

- explaining the correct use of the investigational product(s) to the site personnel,
- verifying that instructions are followed properly,
- maintaining accurate records of investigational product dispensing and collection,
- and returning all unused medication to Lilly or its designee at the end of the study.

Note: In some cases, sites may destroy the material if, during the investigative site selection, the evaluator has verified and documented that the site has appropriate facilities and written procedures to dispose of clinical trial materials.

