The Lilly clinical pharmacologist or clinical research physician/scientist will monitor safety data throughout the course of the study.

Lilly will review SAEs within time frames mandated by company procedures. The Lilly clinical pharmacologist or research physician will consult with the functionally independent Global Patient Safety therapeutic area physician or clinical research scientist when appropriate, and periodically review:

- trends in safety data
- laboratory analytes
- AEs including monitoring of incidence of and nature of any infections, infusion reactions, and injection site reactions.

9.4.6. *Injection / Infusion-Site Assessments*

Local tolerability at the injection or infusion site will be evaluated for erythema, induration, categorical pain, pruritus, and edema as indicated in the Section 2 and reported in the CRF. If one or more symptom(s) of an injection/infusion site reaction is reported during the assessment, a single AE for injection or infusion site reaction will be recorded on the AE page of the CRF.

In addition, pain measurements will be quantified using the the 100-mm validated Visual Analog Scale (VAS) for the subjects receiving Test SC 2 x 1 mL and the Test SC 1 x 2 mL formulation. The VAS is a well-validated tool (Williamson and Hoggart 2005) to assess injection-site pain presented as a 10-cm (100-mm) line, anchored by verbal descriptors, usually “no pain” and “worst imaginable pain.” The patient will be asked to rate any pain on a scale of 0 to 100 mm on the line immediately (within 1 minute) following the start of the injection and at time points according to the Schedule of Activities (Section 2). For the Test SC 2 x 1 mL formulation, the pain assessment will be done only for the first of the 1 mL injections.

Injection site leakage for the Test SC 1 x 2 mL and the first of the Test SC 2 x 1 mL injections will be assessed using pre-weighed filter paper, blotting the injection site immediately after the injection to absorb any post-injection leakage and placing the filter paper back on the tared analytical balance in a similar manner as previously described (Ignaut and Fu 2012). For the Test SC 2 x 1 mL formulation, the leakage assessment will be done only for the first of the 1 mL injections. The amount of leakage will be calculated by subtracting the pre-weighed filter paper measurement from the post-injection site blot filter paper measurement. Any bleeding from the injection site will also be documented.

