9.4.8 Injection Site Leakage

Injection site leakage data will be listed. Any bleeding from injection site will also be documented (performed only on subjects randomized to Test SC 2 × 1 mL and Test SC 1 × 2 mL).

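### Injection-site bleeding is prompted in the two Test SC arms but not in Reference, so ascertainment is unequal for the formulation comparison of tolerability (minor)

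*Protocol*

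**What the plan says.** **Where bleeding is looked for.** The only scheduled bleeding check is the 0-hour leakage and bleeding assessment in the Schedule of Activities: "Performed only on subjects randomized to Test SC 2 x 1 mL and Test SC 1 x 2 mL only. 0 hour assessments should be" made within 1 minute after injection. SAP 9.4.8 has the same limit: "performed only on subjects randomized to Test SC 2 × 1 mL and Test SC 1 × 2 mL". Protocol 9.4.6 adds "Any bleeding from the injection site will also be documented" at the end of the paragraph on weighing leakage in the Test SC arms. In the 2 × 1-mL arm, leakage is assessed for the first injection only. The text does not say whether the same holds for bleeding.

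**What all arms share.** Protocol 9.4.6: "Local tolerability at the injection or infusion site will be evaluated for erythema, induration, categorical pain, pruritus, and edema". Bleeding is not on this list. For SC subjects the Schedule places this assessment at 0, 0.25, 24, 168 and 336 hours. The 0-hour assessment falls within 5 minutes after all SC injections.

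**What the data are for.** A secondary objective in Protocol Table AMAL.1 is "To assess the impact of Drug Product formulation changes and number of injections on tolerability of LY3074828". Its endpoints are the incidence of TEAEs and of treatment-emergent anti-drug antibodies, in all treatments. Protocol 5.4 describes this objective as a comparison between formulations and gives that as a reason for having no placebo arm.

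**How safety is reported.** Adverse events are recorded in every arm (Protocol 9.2) and TEAEs are summarized by treatment (SAP 9.4.1). No inferential safety analysis is planned (SAP 9.4.11).

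**The concern.** Reference is the only control for the SC formulation comparison and has the most needle punctures per subject. It is also the one SC arm in which nobody is prompted to look for bleeding. In the Test SC arms, staff look within a minute of injection.

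When one side of a comparison is prompted and the other is not, raw counts partly reflect who was asked. Safety results will be read as raw counts by treatment in an open-label study, so the difference in prompting would not be visible in the tables. A bleeding count that is higher in Test could come from the extra check, and a truly higher burden from the three-injection Reference regimen could be missed. The adverse event definition in Protocol Appendix 1 covers any unfavourable, unintended sign. Bleeding that staff judge to be an adverse event could therefore carry the imbalance into TEAE incidence, which is a named endpoint.

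**Working it through.** The plan states no figure for bleeding, so there is none to reproduce. The check has two parts.

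**1. Punctures without a prompted check**

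Inputs: 18 subjects per arm (Protocol 5.1); 3, 2 and 1 injections per subject (Protocol Table AMAL.3).

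- Reference: 18 × 3 = 54
- Test SC 2 × 1-mL: 18 × 2 = 36
- Test SC 1 × 2-mL: 18 × 1 = 18
- Total: 108. Share with no prompted check: 54/108 = 50%.
- If bleeding in the 2 × 1-mL arm follows the first-injection rule for leakage: (54 + 18)/108 = 67%.

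**2. What unequal checking could do (illustration only)**

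Let p be the bleeding risk per puncture, assumed equal in all arms and independent between punctures. Let k be injections per subject. Let q be the share of subjects with bleeding in whom it is recorded. The documents give neither p nor q. Take q = 1 where there is a prompted check at every injection.

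Expected subjects recorded = 18 × [1 − (1 − p)^k] × q

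With equal checking (q = 1 in all arms):

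| p | Reference (k = 3) | Test 2 × 1 (k = 2) | Test 1 × 2 (k = 1) |
|---|---|---|---|
| 2% | 1.1 | 0.7 | 0.4 |
| 5% | 2.6 | 1.8 | 0.9 |
| 10% | 4.9 | 3.4 | 1.8 |
| 20% | 8.8 | 6.5 | 3.6 |

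With p = 10% and unprompted recording in Reference only:

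- q = 50%: 4.88 × 0.50 = 2.4
- q = 25%: 4.88 × 0.25 = 1.2
- q = 10%: 4.88 × 0.10 = 0.5
- q = 0: 0

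Reference falls below Test 2 × 1-mL when q < [1 − (1 − p)²]/[1 − (1 − p)³]. At p = 10% this is 0.190/0.271 = 70%. It falls below Test 1 × 2-mL when q < p/[1 − (1 − p)³], which is 0.100/0.271 = 37%. Under these assumptions the true order can reverse through recording alone. The Reference count is zero only if no bleeding there is ever recorded.

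If only the first injection is checked in the 2 × 1-mL arm, that arm would show 18 × p subjects, the same as the 1 × 2-mL arm (1.8 at p = 10%).

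**The case against.** **Adverse event review covers every arm.** A reader might infer that bleeding recorded as an adverse event can count against Test only, or that it surfaces in Reference only if a subject volunteers it. The documents do not support either reading. Adverse event review includes Day 1 for all subjects, recording is not restricted by arm, and staff inspect Reference injection sites at five scheduled times. This stands, and it limits the point to unequal ascertainment.

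**No stated route into the TEAE table.** Bleeding is to be documented. The rule that creates a single site-reaction adverse event is tied to the five-sign assessment, and SAP 9.4.8 deals with bleeding apart from adverse events. This stands in part: nothing says that bleeding becomes an adverse event, but nothing excludes it, so its handling is left to judgement.

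**The restriction has a purpose.** VAS pain and the leakage and bleeding check are both confined to the two arms that give the same formulation and volume as one or two injections. That is a coherent design for the number-of-injections question. It does not serve the formulation half of the same objective, and the documents give no reason for leaving Reference out of a visual check.

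**Equal checking would not isolate formulation.** Reference also differs from Test SC 2 × 1-mL in punctures (3 against 2), total volume (3.5 against 2 mL) and concentration (72 against 125 mg/mL). This is correct. Per-injection tabulation removes only part of it, so the result needs that caveat.

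**Timing differs.** The Test check is within 1 minute after injection, and the common 0-hour assessment is within 5 minutes after all injections. The fix must use one common time point.

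**Bleeding may be rare.** Related SC events in Study AMAA were Grade 1 injection site pain, and Study AMAD had no injection site reactions. This gives no sign of a bleeding problem and supports a low rating.

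**Conclusion.** The point holds as unequal ascertainment. The prompted bleeding check covers the two Test SC arms only, while Reference carries half of the planned SC punctures. The check supports the comparison of 1 × 2-mL with 2 × 1-mL, subject to the open question about the second injection. It gives no unbiased comparison of Test with Reference, and bleeding recorded as adverse events may be over-represented in Test.

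The size is minor. Bleeding is not a named endpoint, safety analysis is descriptive, and the PK objectives do not depend on this check. The puncture shares come directly from the documents. The expected counts rest on assumed values of p and q, with equal and independent risk per puncture. They show that a reversal is possible, not that it is likely.

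**What to change.** 1. **Schedule of Activities and Protocol 9.4.6.** Add bleeding (yes/no, per injection site) to the existing 0-hour injection-site assessment in all three SC arms, at its existing time of within 5 minutes after all SC injections. Keep the 1-minute leakage and bleeding check in the Test SC arms as a supplementary measure, and state whether its bleeding part covers the second 2 × 1-mL injection.
2. **SAP 9.4.8.** Tabulate the common bleeding item by arm, per injection and per subject. Note that Reference also differs in number of punctures, volume and concentration.
3. **SAP 9.4.1 and 9.4.8.** State that bleeding found only by the Test-only 1-minute check is reported separately and is not counted in the between-arm TEAE comparison.

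The cost is one CRF item at an assessment already done in every SC arm, one Schedule entry and one SAP table. No visit, staff or equipment is added, and the downside is slightly more recording at 0 hour. One limit remains: Test sites are blotted for leakage before the site assessment, which could clear a trace of blood. The common item should therefore be read as bleeding visible at that inspection.
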